#### **11.4.3.4 Analyses of events of special interest**

The number (n) and percentage (%) of patients with each EOSI event will be summarized by treatment group. All events reported by the Investigators on the AE forms for AESI/EOSI will be listed along with the adjudication outcome (if applicable).

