2.1.4 Safety endpoints

The safety analysis will be based on the reported adverse events, hypoglycemia, adjudicated bone fractures, and other safety information, such as BMD data measured by DXA, clinical laboratory data (including bone turnover markers and markers of calcium metabolism), vital signs, electrocardiogram (ECG), and physical examination, etc.

The following safety endpoints will be assessed throughout the 104 weeks of double-blind treatment:

- Adverse events, hypoglycemia (all, severe, and/or documented symptomatic hypoglycemia), EOSI, adverse events of special interest (AESI), AEs leading to discontinuation of IMP, SAEs, and deaths.
- Percent change from Baseline to Weeks 26, 52 and 104 in BMD (lumbar spine, total hip, and femoral neck).
- Proportion of patients with adjudicated bone fractures over 104 weeks.
- Proportion of patients with \geq 3% decline in BMD at Week 104.
- Changes from Baseline in bone turnover markers to Week 26, 52, and 104 (serum bone resorption markers: N-terminal telopeptide of Type 1 collagen [NTX] and β -CTX-1; serum bone formation markers: P1NP and osteocalcin).

- Changes from Baseline in markers of calcium metabolism to Week 26, 52, and 104 (serum: calcium, phosphorus, magnesium, parathyroid hormone [iPTH], 25-hydroxyvitamin D and 1,25-dihydroxyvitamin D; urinary: calcium, phosphorus and magnesium).
- Clinical laboratory results, vital signs results, and 12-lead ECG.

Observation period

The observation period starts from the time when the patient gives informed consent and will be divided into 4 epochs:

- The **screening** epoch is defined as the time from the signed informed consent date up to the first administration of the double-blind IMP.
- The **treatment** epoch is defined as the time from the first administration of the double-blind IMP to the last administration of the double-blind IMP. This epoch includes the 26-week double-blind core treatment period and the 78-week double-blind extension treatment period. The 26-week double-blind core treatment period is the time from the first administration of double-blind IMP to the last administration of double-blind IMP on or before Visit 8/Week 26 (or Day 182 if Visit 8/Week 26 date is missing).
- The **residual treatment** epoch is defined as the time from the last administration of the double-blind IMP up to 10 days (1 day for hypoglycemia) after the last administration of the double-blind IMP.

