The treatment-emergent adverse event (TEAE) period will include both **treatment** and **residual treatment** epochs. (See the TEAE period for the 26-week core treatment period in [Section 2.5.4](#)).

- The **posttreatment** epoch is defined as the period of time starting the day after the end of the treatment-emergent adverse event period up to the last protocol-planned visit or the resolution/stabilization of all serious adverse events (SAE), adverse events of special interest (AESI) and events of special interest (EOSI), whichever is later.

The **on-study observation period** is defined as the time from start of double-blind treatment until the end of the study (defined as the last scheduled visit for those who completed the study and the date collected on e-CRF page “Completion of End of Study/Follow-up” for those who did not complete the study).

The **post-study observation period** is defined as the time from the day after the end of the study until the resolution/stabilization of all SAE, AESI and EOSI if applicable.

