2.4.5.2 Analyses of hypoglycemia

Analyses of hypoglycemia will be performed on the TEAE period as defined in [Section 2.1.4](#). Hypoglycemia will be classified as severe hypoglycemia, documented symptomatic hypoglycemia, asymptomatic hypoglycemia, probable symptomatic hypoglycemia or relative hypoglycemia (See [Section 2.1.4.1](#)).

The number (%) of patients with 1) any hypoglycemia, 2) severe hypoglycemia and documented symptomatic hypoglycemia will be summarized respectively by treatment group during the TEAE period, as well as the incidence rate in patient years. Two types of incidence rates will be presented: the number of patients with event(s) per 100 patient-years (calculated as the number of patients with at least 1 event/ total exposure in 100 patient-years) and the total number of events per 100 patient-years (calculated as the total number of events / total exposure in 100 patient-years). Note: Note: here exposure in days is duration of treatment-emergent AE period, ie, duration of IMP treatment in days +1 ([Section 2.1.4](#)).

The summary of frequency and incidence rate in patient-years for severe hypoglycemia or documented symptomatic hypoglycemia will be provided as appropriate by gender, age group (≥ 55 to < 65 , ≥ 65 years), race (White, Black or African American, Asian, Other).

A KM curve will be provided by treatment group for the time to first severe hypoglycemia or documented symptomatic hypoglycemia during the TEAE period for the 104-week entire treatment period only (see [Section 2.4.5](#)).

Documented symptomatic hypoglycemia may be presented by ≤ 70 mg/dL (3.9 mmol/L) and < 54 mg/dL (3.0 mmol/L) respectively, as appropriate.

A listing of patients for all events reported on the dedicated e-CRF “Hypoglycemic event information” page will be provided with each category flagged (ie, severe hypoglycemia, documented symptomatic hypoglycemia, asymptomatic hypoglycemia, probable symptomatic hypoglycemia and relative hypoglycemia).

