2.4.5.3 Analyses of adverse events

Generalities

The primary focus of adverse event reporting will be on treatment-emergent adverse events. Pretreatment and posttreatment adverse events will be described separately.

If an adverse event date/time of onset (occurrence, worsening or becoming serious) is incomplete, an imputation algorithm will be used to classify the adverse event as pretreatment, treatment-emergent, or posttreatment. The algorithm for imputing date/time of onset will be conservative and will classify an adverse event as treatment emergent unless there is definitive information to determine it is pretreatment or posttreatment. Details on classification of adverse events with missing or partial onset dates are provided in [Section 2.5.3](#).

Adverse event incidence tables will present the number (n) and percentage (%) of patients experiencing an adverse event by SOC, HLGT, HLT, and PT, sorted by the internationally agreed order for SOCs and alphabetical order for HLGT, HLT and PT within the SOC. Multiple occurrences of the same event in the same patient will be counted only once in the tables within a treatment phase. The denominator for computation of percentages is the safety population within each treatment group.

Sorting within tables ensures the same presentation for the set of all adverse events within the observation period (pretreatment, treatment-emergent, and posttreatment). For that purpose, the table of all treatment-emergent adverse events presented by primary SOC and PT (sorted by the internationally agreed SOC order and decreasing frequency of PTs within SOCs in the sotagliflozin 400 mg group) will define the presentation order for all other similar tables unless otherwise specified. In case of equal frequency regarding PTs, alphabetical order will be used.

Analysis of all treatment-emergent adverse events

The following treatment-emergent adverse event summaries will be generated for the 26-week core treatment period and the 104-week entire treatment period respectively, for the safety population.

- Overview of treatment-emergent adverse events, summarizing number (%) of patients with any:
 - TEAE,
 - Serious TEAE,
 - TEAE leading to death,
 - TEAE leading to permanent treatment discontinuation.
- All treatment-emergent adverse events by primary SOC, showing number (%) of patients with at least 1 treatment-emergent adverse event, sorted by internationally agreed order of primary SOC.

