- TEAEs (PTs with an incidence $\geq 5\%$ in any treatment group) by primary SOC, HLGT, HLT, and PT, sorted by internationally agreed order of SOCs. The other levels (HLGT, HLT, PT) will be presented in alphabetic order.

Analysis of all treatment emergent serious adverse event(s)

- All treatment-emergent serious adverse events by primary SOC, HLGT, HLT, and PT, showing the number (%) of patients with at least 1 serious treatment-emergent adverse event, sorted by the internationally agreed SOC order. The other levels (HLGT, HLT, PT) will be presented in alphabetical order.
- All treatment-emergent serious adverse events regardless of relationship and related to IMP, by primary SOC, HLGT, HLT, and PT, showing the number (%) of patients with at least 1 treatment-emergent serious adverse event, sorted by the internationally agreed SOC order. The other levels (HLGT, HLT, PT) will be presented in alphabetical order.

Analysis of all treatment-emergent adverse event(s) leading to treatment discontinuation

- All treatment-emergent adverse events leading to treatment discontinuation, by primary SOC, HLGT, HLT, and PT, showing the number (%) of patients sorted by the

internationally agreed SOC order. The other levels (HLGT, HLT, PT) will be presented in alphabetical order.

Analysis of adverse events of special interest

The summaries of AESI will be presented for the 104-week entire treatment period only in the safety population.

Pregnancy and overdose will be included in overall AE summaries if any are reported. ALT increase >3 x ULN is included in laboratory PCSA summary if any.

In addition, the number (%) of patients with an AESI will be summarized by PT and by treatment group. Corresponding listings will be provided as appropriately.

Analysis of events of special interest

The summaries of EOSI will be presented for the 104-week entire treatment period only in the safety population.”

CV events, bone fracture and DKA

For EOSIs that are adjudicated (ie, deaths, myocardial infarction, stroke, and unstable angina requiring hospitalization, heart failure requiring hospitalization, bone fracture, and diabetic ketoacidosis), the number (%) of patients with an EOSI positively adjudicated by CEC will be summarized by treatment group. All EOSIs sent for adjudication and/or reported by the Investigators in the specific AE forms will be listed along with the adjudication outcome.

Renal events

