For the EOSI renal events where selected events are adjudicated, the number (%) of patients with any renal events identified in [Table 3](#) in [Section 2.1.4.2](#) will be summarized by treatment group.

The following renal events will be listed along with the adjudication outcome if applicable, including events,

- i. Recorded in eCRF “GFR decrease”.
- ii. Recorded in eCRF “Renal Event – Dialysis”.
- iii. Identified as “Renal transplant” in eCRF “Other procedure”, where adjudication is not required.

Renal death will be part of all deaths specified above.

Other EOSIs

For EOSIs that are not adjudicated, the number (%) of patients with at least one event will be summarized by treatment group and by PT (as identified in [Table 3](#) in [Section 2.1.4.2](#)).

Severe hypoglycemia will be included in the summary of hypoglycemia (See [Section 2.4.5.1](#)).

AE leading to an amputation is described in the section below.

Analysis of Amputation:

The number (%) of patients with amputation will be summarized by treatment group and by PT and LLT during the study (ie, regardless of on- or post-treatment). Amputation is a procedure recorded in eCRF form “Other Procedures related to Amputation”. Patients who had a procedure related to amputation will be listed.

The number (%) of patients with an “AE leading to an amputation” will be summarized by treatment group and by PT. The “AE leading to an amputation” is determined by the AE identifier recorded in eCRF “Other Procedures related to Amputation” when “AE correction” is chosen as the reason for the amputation procedure.

In addition, the number (%) of patients with an “AE potentially leading to an amputation” will be summarized by treatment group and by PT (as identified in [Table 2](#) in [Section 2.1.4.2](#); these PTs in [Table 2](#) were requested by the European Medicines Agency/ Pharmacovigilance Risk Assessment Committee[EMA/PRAC] Assessment Report 9 February 2017). The associated list will be provided as well, with patients who had an amputation procedure flagged. “AE potentially leading to amputation” represents the condition that commonly precedes amputation procedure, but not in all cases an amputation has occurred (as per the EMA/PRAC request).

Analysis of pretreatment and posttreatment adverse events

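### Adjudicated fractures over 104 weeks are to be reported only as a crude percentage of treated patients, which ignores incomplete follow-up and so understates the 104-week risk

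*SAP*

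**What the plan says.** SAP 2.1.4 lists as a safety endpoint the "Proportion of patients with adjudicated bone fractures over 104 weeks"; Protocol 9.2 has the same item. For adjudicated events of special interest, fractures among them, SAP 2.4.5.3 plans that "the number (%) of patients with an EOSI positively adjudicated by CEC will be summarized by treatment group". Protocol 11.4.3.4 says no more: "patients with each EOSI event will be summarized by treatment group". The general rule for adverse event tables in SAP 2.4.5.3 is that "The denominator for computation of percentages is the safety population within each treatment group". On period, "The summaries of EOSI will be presented for the 104-week entire treatment period only in the safety population".

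Other outcomes get more. For hypoglycemia, "Two types of incidence rates will be presented", both per 100 patient-years, with a Kaplan-Meier curve (SAP 2.4.5.2). Kaplan-Meier displays are also planned for treatment discontinuation (SAP 2.2) and rescue (SAP 2.4.4.3). The censoring table in SAP 2.5.4 covers those three outcomes and has no row for fracture. Appendix C lists no fracture analysis.

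The counting window for fractures is not stated outright. SAP 2.4.5 applies the observation periods of SAP 2.1.4 to safety analyses in general, and there "The treatment-emergent adverse event (TEAE) period will include both" the treatment epoch and the residual epoch, which ends 10 days after the last dose. For amputation the SAP is explicit that events count "during the study (ie, regardless of on- or post-treatment"). Fractures have no such wording.

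**The concern.** A proportion over 104 weeks is a risk over a fixed time. Dividing patients with a confirmed fracture by everyone treated estimates that risk only if everyone is observed for 104 weeks. Otherwise, someone who leaves at Week 10 without a fracture is counted as having completed two fracture-free years.

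Two things are at stake. Within each arm, any loss of follow-up pulls the percentage below the risk that it is named for. Between arms, unequal loss shifts the comparison.

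A further problem arises at the first-step analysis, whose results go into the submission dossier. Under SAP 3, ongoing patients are counted up to a common cut-off date, so their follow-up runs from about 26 weeks upward according to when they enrolled. A crude percentage of adjudicated fractures at that point refers to no defined period. Protocol 4.4 describes the study as specifically designed to evaluate bone health, so its clinical bone outcome merits at least the treatment given to hypoglycemia.

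**Working it through.** **Plan's own figures.** There is none for fractures: no rate, event count or power. The only loss figure is the 30% missing rate used to size the BMD comparison (SAP 1.3). It is not arm-specific and does not describe fracture follow-up. Loss and fracture risk below are therefore assumptions, shown as ranges. The 120 patients per arm come from SAP 1.3.

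**Check 1: loss spread evenly over 104 weeks.** Let R be the true 104-week risk and d the share lost. With a constant and low hazard, a lost patient is observed for half the period on average and contributes about R/2. So

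crude ≈ (1 − d)R + d(R/2) = R(1 − d/2).

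With R = 4% assumed, 120 × 0.04 = 4.8 fracture patients are expected per arm under full follow-up.

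| Loss d | 1 − d/2 | Crude % | Shortfall per 120 |
|---|---|---|---|
| 10% | 0.95 | 3.8 | 0.24 |
| 20% | 0.90 | 3.6 | 0.48 |
| 30% | 0.85 | 3.4 | 0.72 |
| 40% | 0.80 | 3.2 | 0.96 |

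**Check 2: constant dropout hazard.** Take T = 728/365.25 years, fracture hazard λ, and dropout hazard g = −ln(1 − d)/T. Then

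crude = λ/(λ + g) × [1 − exp(−(λ + g)T)], against a true risk of 1 − exp(−λT).

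For λ = 2% per year the true risk is 3.91%. The crude value at d = 30% is 3.29%, a ratio of 0.84 and a shortfall of 0.74 patients. The ratios at 10%, 20% and 40% are 0.95, 0.90 and 0.78; the shortfall at 40% is 1.01 patients. For hazards of 1% to 5% per year the ratios are nearly unchanged.

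**Between arms, no true difference (check 1).**
- Equal loss: ratio 1.00.
- Sotagliflozin 40%, placebo 20%: 0.80/0.90 = 0.89.
- Sotagliflozin 20%, placebo 40%: 0.90/0.80 = 1.13.

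**Between arms, true hazard ratio 1.5, λ = 2% per year on placebo (check 2).** The true risk ratio is 1.49. It appears as 1.32 with 30% loss on sotagliflozin and 10% on placebo, and as about 1.7 with the losses reversed.

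**First step.** With R = 4% and a constant hazard, the risk over t weeks is 1 − 0.96^(t/104): about 1.0% at 26 weeks and 2.0% at 52. The crude percentage is a mixture of such values, with weights set by the enrolment pattern.

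**Counting window.** The same formula applies, but d changes meaning. On an on-study count, d is the share leaving the study. If counting stops 10 days after the last dose, d is the share stopping treatment, which is at least as large. If those shares were, say, 10% and 30%, the shortfall would go from about 5% to about 15%.

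**The case against.** The strongest reply is that the protocol works hard to prevent this loss. Rescued patients continue blinded treatment and stay in the study (Protocol 8.2.2). A BMD fall beyond the stated threshold ends treatment, not participation (Protocol 10.3.3). Patients who stop treatment are to be followed to the scheduled end (Protocol 10.3.4; SAP 1.1), and those who refuse visits are telephoned for adverse events. This stands: on an on-study count, only withdrawal from the study matters. It does not settle the matter, because withdrawal is allowed and the SAP does not say that the on-study count is the one used.

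A reader might infer that the plan would hide a fracture excess on sotagliflozin, with placebo patients leaving for poor control and active patients leaving under the BMD rule. The documents do not support this. Those routes do not end follow-up, nothing predicts unequal loss, and the bias could go either way. Adjudicated events are listed with their outcome, exposure in patient-years is reported, and discontinuations are shown by arm, so a marked imbalance would be visible.

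Nor is a between-arm estimate wholly absent: SAP 2.4.5 allows relative risks with 95% confidence intervals. They are optional, however, and no exposure adjustment is stated.

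Precision also limits the stakes. With five fracture patients in each arm of 120, the standard error of the log risk ratio is √[2(1/5 − 1/120)] = 0.62. The 95% interval around 1.0 is then about 0.3 to 3.4, and a shift to 0.89 lies far inside it. Finally, staggered entry should be balanced by randomization, so the first-step problem concerns what the percentage means more than the comparison.

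**Conclusion.** The point holds as a choice of estimator. The planned percentage does not estimate the 104-week risk once follow-up is incomplete, and nothing committed to in the SAP makes up for this. The relative understatement is about 5% to 20% for 10% to 40% loss (up to 22% with a constant dropout hazard). At an assumed risk near 4% that is about one patient per arm or fewer. Bias in the comparison depends on unequal loss, which the documents neither predict nor rule out, and its direction is open.

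The size rests on assumed loss and fracture rates, a constant fracture hazard, and dropout unrelated to fracture risk. It grows if counting stops shortly after the last dose, which the SAP leaves unclear. The change is worth making because it is cheap and the outcome is central to the trial. A conclusion that the fracture comparison is invalid would go beyond the evidence.

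**What to change.** In SAP 2.4.5.3, state that CEC-confirmed fractures are counted over the on-study period, with an on-treatment version as support. Add by arm:

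- first fractures per 100 patient-years at risk;
- the 104-week cumulative incidence from time to first fracture (Kaplan-Meier, or with death as a competing event);
- the difference from placebo with a 95% confidence interval for each dose.

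Add a fracture row to the censoring table in SAP 2.5.4: end of follow-up for the final analysis, and the common cut-off date for patients still ongoing at the first step. At the first step, report the rate and the cumulative incidence only as far as follow-up allows. Keep the crude number and percentage as a supportive line.

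The cost is SAP wording, one table and one plot, using dates already collected and conventions already written for hypoglycemia; the competing-event version needs a little more code. Intervals will be wide because events are few. The new estimates still assume that censoring is unrelated to fracture risk, so they reduce the problem without removing it if patients at higher risk leave selectively.

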2.4.5.4 Deaths

The following summaries of deaths will be generated for the safety population.

- Number (%) of patients who died by study period (on-study, during TEAE period, poststudy).
- Deaths in nonrandomized patients or randomized but not treated patients.
- Treatment-emergent adverse events leading to death (death as an outcome on the adverse event case report form page as reported by the Investigator) by primary SOC, HLG, HLT, and PT showing number (%) of patients sorted by internationally agreed SOC order, with HLG, HLT, and PT presented in alphabetical order within each SOC.

2.4.5.5 Analyses of laboratory variables

Laboratory parameters will be grouped and summarized by biological function as described in [Section 2.1.4.4](#).

The summary statistics (including number, mean(standard deviation), median, Q1, Q3, minimum and maximum) of all laboratory variables (central laboratory values and changes from Baseline, and/or percent change from Baseline [eg, lipid parameters])) will be calculated for each planned visit or study assessment (screening, Baseline, post-Baseline time point, last on-treatment) by treatment group.

The incidence of PCSAs (list provided in Appendix A) at any time during the treatment-emergent adverse event period will be summarized by biological function and treatment group whatever the baseline level and/or according to the following baseline status categories:

- Normal/missing.
- Abnormal according to PCSA criterion or criteria.

In that case only the worsening of the worst case are presented.

For parameters for which no PCSA criteria are defined, similar table(s) using the normal range will be provided.

All measurements collected during the TEAE period, including values from unscheduled visits, will be considered for the PCSA summaries. The summary tables will include patients in the safety population that have at least one assessment performed during the TEAE period. When PCSA criteria are based on change from Baseline, patients must have non-missing baseline to be included in the summary. And when required by the definition of the abnormality, patients must also have available laboratory normal ranges.

A listing of patients with at least one post-Baseline measurement PCSA or out of normal range (when no PCSA is defined) will be provided and will display the patients' entire profile over time for parameters belonging to the corresponding biological function. Individual data listings will include flags when applicable:

- Baseline values will be flagged "B".
- Normal laboratory ranges, available for most laboratory parameters, will be identified as ULN and LLN. Baseline, last on-treatment value, and individual data will be flagged "L" if the value is below the LLN and will be flagged "H" if it is above the ULN.
- Laboratory PCSA criteria will be used for the corresponding laboratory parameters. Values reaching a PCSA limit will be flagged (+, ++, -, or -- depending upon the direction and level of the abnormality). Flags for WBC and differential counts will be determined using data expressed in international units.

For parameters whose PCSA criteria are based on multiples of ULN, the parameter's value will also be expressed as multiples of ULN in the individual data presented.

Drug-induced liver injury

The liver function tests, namely AST, ALT, alkaline phosphatase, and total bilirubin, are used to assess possible drug-induced liver toxicity. The proportion of patients with PCSA values at any post-Baseline visit by baseline status will be displayed by treatment group for each parameter. The proportion of patients with PCSA values at any post-Baseline visit will also be displayed by duration of exposure for each treatment group (only if a tabulation summary is necessary).

Listing of possible Hy's law cases identified by treatment group (eg, patients with any elevated ALT > 3 x ULN, and associated with an increase in bilirubin ≥ 2 x ULN) with ALT, AST, alkaline phosphatase and total bilirubin and the following complementary parameters if available: conjugated bilirubin and prothrombin time/international normalized ratio, creatine phosphokinase, serum creatinine, complete blood count, anti-HAV IgM, anti-HBc IgM, anti-HCV and HCV RNA, anti-CMV IgM and anti-HEV IgM antibodies, auto-antibodies: anti-nuclear, anti-DNA, anti-smooth muscle, Epstein-Barr virus, herpes viruses, and anti-LKM..

